The sample size was calculated based on results obtained from previous studies of similar nature. Sample size was estimated assuming alpha error= 5% and study power= 80%. Tekin et al ⁽³⁶⁾ reported mean \pm SD Sound, Eye and Motor (SEM) score = 3.93 ± 1.223 when intraligamentary anesthesia (ILA) was used, and 5.17 ± 1.891 when inferior alveolar nerve block (IANB) was used. Based on comparison of means, sample size was calculated to be 25 per group, and the total sample size required to compare the effectiveness of CC-ILA technique versus IANB during extraction of primary mandibular molars = number of groups \times number per group= $2 \times 25 = 50$.⁽⁴¹⁾ The sample size was calculated using powerandsamplesize.com calculator.⁽⁴²⁾

Criteria for sample selection:

a) Eligibility Criteria

- Age range from 5 – 7 years.
- Children free of any systemic disease or special health care need (ASA I).⁽⁴³⁾
- No previous bad dental experience.⁽⁴⁴⁾
- Positive or definitely positive behaviour during preoperative assessments according to the Frankl Rating Scale (score 3 or 4) (Appendix I).⁽⁴⁵⁾

- Patients whom their mandibular primary molars are indicated for extraction:^(46, 47)
 - Clinical signs and symptoms of pulp degeneration, such as swelling or sinus tracts.
 - Radiographic evidence of periapical or interradicular radiolucency.
 - Non restorable crowns.
 - Failed pulpotomies.
- Patients whose parents will give their consent to participate.

b) Exclusion Criteria for teeth ⁽⁴⁸⁾

- Root resorption affecting more than one third of the root length.
- Fractured roots due to trauma.
- Signs of mobility.
- Ankylosed roots.
- Active sites of pathosis in area of injection that could affect anaesthetic assessment.
- History of allergy to local anesthesia.

Materials

- a) Topical Anaesthesia – Benzocaine gel 20%.*
- b) 27-guage long anaesthetic needles.**
- b) Local anaesthetic carpules: Articaine hydrochloride 4% with adrenaline 1:100,000.***
- c) Equipment:
 - Wand - STA Single Tooth Anaesthesia Device (Figure 2)****
 - Disposable Wand – STA Handpieces with 30-guage 0.5-inch needles. ****
 - Pulse oximeter.*****
 - Dental anaesthetic syringe (non-disposable breech loading, metallic cartridge type).*****
 - Lower Full-crown Extraction forceps.*****

* Dharma Research, Inc. [name].

** C-K Ject, CK Dental Ind. Co., LTD., Korea.

*** ARTINIBSA, Inibsa Dental S.L.U, [name].

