- The second observer will be trained separately to assess pain using (SEM) scale by observing children undergoing dental procedures and classifying the child's behavior on videotapes. After a 7-day interval, the exercise will be repeated in order to develop an acceptable degree of examiner reliability. Intra-examiner reliability will be tested by Intraclass correlation (ICC).⁽⁵¹⁾

Clinical Procedure

Preliminary screening visit

- Full medical and dental history will be carried out to select patients. Those patients whose parents will give their consent to participate will be examined.⁽⁵²⁾ Proper diagnosis with thorough clinical examination, and intraoral periapical radiograph of the tooth to be extracted will be taken to ensure that the patient will match the inclusion criteria.

Patient Preparation ⁽⁵³⁾

- The child's dental visit will be a mean of introducing dentistry and acquainting the child to the dental unit and dental instruments using 'Tell Show Do' technique. No treatment will be done to the child in order to build a strong patient-dentist relationship.⁽⁵⁴⁾

Intervention Visit

Psychological child preparation:

- The children will be told that their teeth will be put to sleep after placing some jelly and feeling a little pinch, in order to get rid of germs.
- Audible sounds will be heard while using STA in group I, so they must be informed.
- Subjects in Group II (IANB) will be told that their cheek will feel big and funny for some time.
- The procedure will be videotaped as a method of motivation to document their good behaviour.
- Patients will be positioned in supine position with the head and chest parallel to the floor and the feet slightly elevated.
- Mouth props may aid in maintaining a wide mouth opening.
- For both groups, soft tissues will be dried using (2 x 2 cm) gauze to enhance the absorption of the topical anaesthetic. Twenty percent Benzocaine topical anaesthetic gel will be used to obtund the discomfort associated with needle insertion. It will be applied at the site of needle penetration and left in contact with the soft tissues for one minute to optimise its effect.

Local Anaesthesia Administration

a) Wand-STA system:

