Heart rate (HR) is a physiological sign of pain.⁽⁵⁷⁾ It will be measured using a pulse oximeter. A brief demonstration using the pulse oximeter will be done, and the patient will be instructed to stay still and not to move his hands a lot in order to obtain accurate readings. The pulse oximeter will be placed on the patient's index finger to measure the baseline heart rate (before giving the LA), another measurement will be recorded during LA administration, and during extraction. Readings will be recorded at 2-minute intervals and the mean heart rate measurement will be calculated.

B. Objective method:

Sound, Eye, Motor (SEM) Scale (Figure 3), will be used as an objective method for pain assessment during LA administration and extraction. It comprises the following parameters: (1) Sound, (2) Eye, (3) Motor. For each child, the sounds, eye symptoms and body movements will be evaluated independently by a blind impartial observer using the recorded video tapes. The slightest manifestation of the sound, eyes, or motion of the patient is graded in four levels: comfort, mild, moderate, and severe discomfort, and subsequently given grades 1, 2, 3, 4, respectively. SEM score will be calculated by summing the three grades of the parameters. ⁽⁵⁸⁾

Parameter	Comfort	Mild discomfort	Moderate discomfort	Severe discomfort
Grade	1	2	3	4
Sound	No sound	Non-specific sound (probable pain)	Verbal complaint, louder sound	Verbal complaint shouting, crying
Eye	No sign	Dilated eye without tears (anxiety sign)	Tears, sudden eye movements	Crying, tears all over the face
Motor	Relaxed body and hand status	Muscular contraction, contraction of hands	Sudden body and hand movements	Hand movements for defence, turning the head to the opposite side

Figure (3): SEM scale for the assessment of children's behaviour

Subjective method:

A modified face scale⁽⁵⁹⁾ (Figure 4) from the Maunuksela et al⁽⁶⁰⁾ scale will be used to subjectively record pain during LA injection and extraction. It consists of three schematic faces with different facial expressions for happy and sad faces representing: (A) satisfaction; (B) indifference; and (C) dissatisfaction, respectively. Each child will be trained to use the scale by modelling and then asking each participant to think of the last time she/he felt something painful and to select the facial expression that best represented his/her experience of discomfort.

[figure not shown]

Figure (4): Faces scale modified from the Maunuksela et al scale.

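### If children are told that the film records their good behaviour, they are encouraged to hold back the signs from which SEM is scored

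*Combined protocol and SAP*

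**What the plan says.** In the combined protocol and SAP, the list headed Psychological child preparation (Intervention Visit) includes this item: "The procedure will be videotaped as a method of motivation to document their good behaviour". It is not limited to one arm.

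Under Study Outcomes, Objective method, SEM "will be used as an objective method for pain assessment during LA administration and extraction". Each child is "evaluated independently by a blind impartial observer using the recorded video tapes". No other recording of the participants is described, so the motivational film and the measurement film are the same.

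The scale is meant to be sensitive: "The slightest manifestation of the sound, eyes, or motion of the patient is graded in four levels". The graded items include complaints, crying, tears, hand contraction and sudden or defensive movement. Each of the three parameters is graded 1 to 4 and the grades are summed, so the score runs from 3 to 12.

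The eligibility criteria admit children aged 5 to 7 with Frankl scores of 3 or 4. Sample size estimation uses SEM means and SDs from an earlier study: "3.93 ± 1.223 when intraligamentary anesthesia (ILA) was used" and "5.17 ± 1.891 when inferior alveolar nerve block (IANB) was used".

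The plan gives no neutral wording for the filming. It does not say that the child may show that something hurts, and it does not discuss how the framing might affect SEM.

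**The concern.** For a child in a dental chair, behaving well is most naturally understood as not crying out, not crying and not moving about. Those are the three things SEM grades. A film offered as evidence of good behaviour therefore acts on the outcome as well as recording it, and the score may partly reflect how well the child performs for the camera. Children selected for cooperation are plausibly the ones most likely to respond to such a prompt.

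Absolute SEM levels would then sit lower than the pain warrants in both arms. The between-arm difference could also narrow, because the arm with more pain has more signs to hide. No analysis can repair this afterwards, since a suppressed sign leaves no trace on the tape.

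**Working it through.** **Inputs.** From Sample size estimation: ILA mean 3.93, SD 1.223; IANB mean 5.17, SD 1.891; difference 5.17 − 3.93 = 1.24; 25 per group; alpha 5% (taken as two-sided, since the plan does not say); power 80%. From the SEM table: minimum score 3 × 1 = 3.

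**The plan's own figure.** Use n = 2(1.960 + 0.842)² × SD² / 1.24².
- With the simple average SD, (1.223 + 1.891)/2 = 1.557, n = 24.7, which rounds up to 25. This matches the plan.
- With the root-mean-square SD, √[(1.223² + 1.891²)/2] = 1.592, n = 25.9, which rounds up to 26.

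**Room above the floor.** ILA: 3.93 − 3 = 0.93 points, or 0.93/1.223 = 0.76 SD. IANB: 5.17 − 3 = 2.17 points.

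**Suppression model A: random hiding.** Let X = SEM − 3 have mean m and variance v, and let each sign-point be hidden with probability s in both arms. Then the mean becomes m(1 − s) and the variance becomes (1 − s)²v + s(1 − s)m. The starting variances are 1.223² = 1.496 and 1.891² = 3.576. Power is from the unequal-variance t-test (noncentral t), two-sided 0.05, 25 per group.

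Worked example, s = 0.2:
- ILA variance: 0.64 × 1.496 + 0.16 × 0.93 = 1.106.
- IANB variance: 0.64 × 3.576 + 0.16 × 2.17 = 2.636.
- Standard error: √[(1.106 + 2.636)/25] = 0.387.
- Difference: 1.24 × 0.8 = 0.992. Ratio: 0.992/0.387 = 2.56. Power: 0.707.

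| s (assumed) | ILA mean | IANB mean | Difference | Power, model A | Power, model B |
|---|---|---|---|---|---|
| 0 | 3.93 | 5.17 | 1.24 | 0.767 | 0.767 |
| 0.1 | 3.84 | 4.95 | 1.12 | 0.739 | 0.767 |
| 0.2 | 3.74 | 4.74 | 0.99 | 0.707 | 0.767 |
| 0.3 | 3.65 | 4.52 | 0.87 | 0.668 | 0.767 |

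The starting 0.767 is below 80% because this test uses each arm's own SD and the t distribution. The film plays no part in that gap.

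**Suppression model B: exact proportion.** Every child's excess is multiplied by (1 − s). The difference and both SDs shrink by the same factor, so their ratio stays at 1.24/√[(1.496 + 3.576)/25] = 2.75. Power does not move, although the means and the difference fall exactly as in model A.

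In both models the means and the difference fall. Only the random-hiding model loses power.

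**The case against.** **The child's script is not given.** Neighbouring items state what children are told or must be informed of; the filming item does not. Nothing says children are asked to keep quiet, dry-eyed or still for the camera. This stands, so the point has to be conditional. But the item sits in the child-preparation list, and a film can motivate only a child who knows what it is for.

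**Both arms get the same framing.** A reader might infer that the film favours one technique. The documents do not support that: the item is not arm-specific, allocation is random and one operator treats every child. A reader might also infer that the trial will overstate how far pain was eliminated. The primary aim is stated as a comparison with IANB, so a common lowering affects absolute levels and does not by itself mislead about which technique is better.

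**A power loss is not established.** The fraction s has no source in the documents, and random hiding adds variance by construction. Even the narrowing of the difference depends on the pattern. If mild signs can be hidden but crying and defensive movements cannot, the difference need not shrink. This stands in full.

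**Comparability with the sizing study.** It is tempting to add that the framing makes SEM here unlike SEM in the study behind the sample size. The plan reports only that study's results and does not say how its children were prepared or filmed, so this cannot be claimed.

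**Other pain measures exist.** Heart rate is not under the child's voluntary control, and the face scale is a separate self-report. This softens the problem without removing it, because the sample size rests on SEM.

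**Conclusion.** The point holds as a measurement-validity weakness that is cheap to remove. The film used to score SEM is also described as motivation for good behaviour, and good behaviour overlaps with the absence of the signs SEM grades. If children are given that framing, SEM levels can be pushed towards 3 in both arms and the between-arm difference may shrink. It is not a directional bias.

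The size is unknown. The range shown, from no change in power to a fall from 77% to 67%, rests on an assumed s of 10% to 30%, an equal effect in both arms, the planning means and SDs, and a two-sided 5% test. These figures illustrate what could happen and do not predict it. They give no reason to change the sample size.

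**What to change.** In Psychological child preparation, replace the filming item with a neutral statement, identical in both arms, that the visit will be filmed so the researchers can look at it later. Add that staff will not link the film to good behaviour until the filmed injection and extraction are over and the face ratings have been taken.

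The cost is one sentence in the child script and one motivational prompt before treatment. The rest of the behaviour guidance, including Tell-Show-Do and the acquaintance visit, is unchanged, as are the filming, the blinded scoring, the sample size and the analysis. Neutral wording leaves the camera in place, so any effect of simply being filmed would remain.

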As the IANB anesthetizes a wide area other than the teeth, patients encounter loss of sensitivity, as well as total or partial loss of function of the facial muscles and tongue for the duration of the anaesthesia which may last up to two hours.⁽¹⁰⁾ Temporary hindering of patients' daily life with limited speech ability, eating, and most importantly, the risk of cheeks and lip biting are major drawback of this technique. Moreover, a rare but major complication of IANB anaesthesia is the injury of the mandibular nerve that could result in permanent impairment of the nerve function.^(11,12)

In an attempt to overcome the limitations of the IANB technique, other methods have been advocated such as Intraligamentary Anaesthesia (ILA). This technique was introduced by Chompret (1920).⁽¹⁶⁾ Intraligamentary Anaesthesia is a method of intra osseous injection with LA reaching the cancellous space in the bone via the periodontal ligament (PDL).

Intraligamentary Anaesthesia can be a very effective alternative technique in children, as it can help lessen the struggle of achieving successful anaesthesia during single tooth treatment.^(17, 18) It can have superior features in cases where anatomical variations are present and eliminating soft tissue injury which is a major concern while using other techniques. Moreover, it aids in treatment if teeth in different quadrants that are being summoned in a single visit, which helps both pediatric dentist and the child to avoid management complications associated with multiple dental visits. Many studies have proven that ILA does not cause any secondary complications if carefully applied. It causes very little pain if at all, rapid onset and allowing to start the dental work immediately.⁽¹⁹⁾

Nevertheless, it is believed that ILA has higher levels of post-operative pain than conventional techniques, and its duration only lasts for around 20 minutes.⁽²⁰⁻²²⁾ Two studies reported periodontal abscesses and deep pocket formation after ILA.^(23, 24) Hence, it should not be used for children suffering from cardiovascular problems as they are at more risk of developing subacute bacterial endocarditis.^(25, 26)

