**** STA; Milestone Scientific, Inc., Livingston, NJ, USA

***** Zacurate, [name].

***** BeehiveSolutionsLtd: [name].

***** Likamed [name].

Figure (2): Wand - STA Single Tooth Anaesthesia Device

Randomization

Participants complying with the inclusion criteria will be randomly assigned using a computer-generated list of random numbers.⁽⁴⁹⁾

Allocation concealment

Each child included in the study will be given a serial number that will be used in the allocation. These numbers will be written in identical sheets of paper with the group to which each child is allocated and placed inside opaque envelopes carrying the respective names of the children.⁽⁵⁰⁾ A trial independent personnel will be assigned to the role of keeping the envelopes and unfolding them only at the time of the local anesthesia injection session so that the group the child is allocated to is concealed from the outcome evaluator.

Grouping

Participants will be randomly and equally allocated to one of the two arms (Figure 1).

- **Group I:** (experimental group n = 25) assigned to CC-ILA.
- **Group II:** (control group n = 25) assigned to conventional injection by IANB.

Blinding

The researcher (operator) who will perform all the injections and extractions as well as record heart rate measurements cannot be blinded to the type of intervention; a second impartial observer (evaluator) will record the Sensory, Eye, Motor (SEM) scale independently.⁽³⁰⁾ The statistician will be blinded to the treatment groups. Since the participants will also be blinded, therefore, the study will be triple-blind.

Examiner reliability

- For standardization, all clinical procedures will be performed by a single operator, who will be trained and calibrated for the Wand – STA system via training sessions by an expert through the manufacturing company, as it is too complex to be applied effectively without more appropriate training. Especially, the coordination between the foot pedal handling and the syringe has shown to be difficult.⁽³³⁾
- Training on heart rate measurement using the pulse oximeter will be also planned.

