- In the experimental group, CC-ILA will be administered using the Wand-STA system according to the manufacturer instructions, which is also concurrent with Mittal and Chopra (2019)⁽³⁰⁾. It works with standardised 1.8 mL local anaesthetic carpules. The distolingual and mesiolingual line angles are the most effective for multi-rooted mandibular teeth.
- The injection is initiated by activating the STA mode when the foot control is tapped. A 30-gauge ultra-short disposable dental needle will be inserted in the PDL through the gingival sulcus at the distolingual line angle of the target tooth first, guided by constant audible tones and visual feedback. The needle should be directed approximately 30° angle to the long axis of the tooth and the bevel facing the alveolar bone. A total of 0.9 mL Articaine hydrochloride 4% with 1:100,000 epinephrine will be injected for each root as shown on a special indicator.
- During the anaesthetic solution delivery, the visual pressure indicator will be observed as the pressure is increasing from the red into the green zone. Tissue blanching may occur, which

suggests that enough LA has been delivered. Injection will be stopped by lightly tapping the foot pedal again. The dentist will wait 5 seconds before needle withdrawal. Same steps will be repeated at the mesiolingual line angle.⁽³¹⁾

b) Conventional technique:

- In the control group, a standard technique for the Inferior Alveolar Nerve Block (IANB) will be used supplemented with long buccal infiltration for the buccal gingiva. While the mouth is open as wide as possible, the index finger palpates the injection site.
- A 27-gauge disposable dental needle will be used to inject Articaine hydrochloride 4% with 1:100,000 epinephrine. The needle will be directed between the two primary molars on the opposite side of the arch, entering the tissues at the level of the occlusal plane or slightly lower until bony resistance is met.
- The needle is withdrawn 2mm to aspirate. Once negative aspiration is checked, the remainder of the solution is slowly deposited. The lip and/or cheek will be shaken as a method of distraction. Approximately 1.0 mL of LA will be delivered near the inferior alveolar nerve.⁽³⁶⁾ Two-thirds the needle length should be inserted.
- The needle is withdrawn, then 0.5 ml as a long buccal infiltration distal to the second primary molar is administered.⁽⁵⁵⁾

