- The operator will wait for 3-5 minutes before commencing dental treatment. Numbness will be tested with a dental probe on the gingiva immediately following the injection, and after each 10 seconds in case of CC-ILA and each 30 seconds in case of IANB till full numbness is declared and the time of onset of the anaesthetic effect will be noticed.
- In both groups, extraction will be accomplished according to AAPD guidelines.⁽⁵⁶⁾ Lower full crown forceps will be used to apply slow continuous palatal/lingual and buccal force allowing for the expansion of the alveolar bone to accommodate the divergent roots and reduce the risk of root fracture.
- Care will be taken to support the mandible with the non-extraction hand.
- If the patient suffered pain at any given time in the experimental group, the procedure will be abandoned immediately, IANB will be administered, and extraction will be carried out.

- Post extraction instructions will be given to the patient. They will be instructed to bite on gauze with firm pressure against the surgical site for 30 minutes. They should not disturb the surgical site or rinse vigorously on the day of extraction. According to the technique used, avoid scratching, or injuring the cheek, lips, or tongue if numbness is felt. They should avoid any physical exercise on the day of extraction. Cold soft food is recommended, as well as drinks to keep the child hydrated but without using a straw.
- Analgesics and/or antibiotics will be prescribed if required.
- Planning for space maintenance will be considered as well. All dental injections and extractions will be administered by the same operator, who will be assisted by a trained dental assistant.

Follow up

Following extraction, follow up after 24-hours will be planned via telephone calls to assess any adverse events.

Study Outcomes

I. Assessment of Child Pain Reaction

In the present study, pain will be assessed using the following 3 methods:

A. Physiologic method:

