(A) satisfaction; (B) indifference; and (C) dissatisfaction

II. Assessment of occurrence of adverse events

Parents will be recalled after 24 hours following extraction during follow-up phone calls. Recovery parameter questions will be asked to ascertain the occurrence of lip and cheek biting, post-operative pain, or any adverse events.

STATISTICAL ANALYSIS

All data will be collected; descriptive quantitative values will be summarised using mean and standard deviation, while count and percentage will be used for qualitative values. The data will be represented by suitable tables and graphs. Comparing between normally distributed data will occur using T- and Paired T-tests, while for not – normally distributed data, Wilcoxon signed-rank and Mann-Whitney U tests will be used.

All statistical analyses will be performed with statistical Package for Social Sciences* (SPSS) software version 21.⁽⁶¹⁾ The significance level will be set at $P < 0.05$.

*SPSS Inc., Version 21.0, Chicago, IL, USA

ETHICAL CONSIDERATIONS

The study will be conducted following the ethical principles for medical research involving human subjects in Declaration of Helsinki.⁽⁶²⁾ Ethical approval will be obtained from the Research Ethics Committee, Faculty of Dentistry, Alexandria University before commencing the study.

The objectives, risks and benefits of the study will be explained to parents/ guardians and a signed informed consent will be obtained prior to treatment. (Appendix II). Verbal consent will be obtained from the children before the intervention.

Parents and children will be given age-appropriate oral hygiene instructions including proper teeth brushing twice a day especially before bedtime, as well as flossing if indicated. These measures will be demonstrated on a model. A fluoridated toothpaste and a brush will be provided to each participant on the day of the treatment.

All needed treatment will be provided to the child including any restorations, space maintainers and fluoride application. Post extraction instructions will be explained well to the parents and patients to ensure good wound healing. All the possible clinical and/or adverse outcomes will be explained to the parents and they will be asked to report immediately if any of them occurs.

PROBLEMS ANTICIPATED

1. Lack of compliance from patients and/or their parents.
2. Drop – out of patients during the follow up period.
3. Difficulty in collecting the proposed sample.

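### Numbness is probed every 10 s in the CC-ILA arm and every 30 s in the IANB arm, so raw onset times should not be compared between arms

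*Combined protocol and SAP*

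**What the plan says.** Under Clinical Procedure, Local Anaesthesia Administration, numbness is tested with a probe on the gingiva straight after the injection in both arms. Testing is then repeated "after each 10 seconds in case of CC-ILA and each 30 seconds in case of IANB till full numbness is declared". Onset is to be taken from these tests: "the time of onset of the anaesthetic effect will be noticed". The same bullet gives the wait before extraction: "The operator will wait for 3-5 minutes before commencing dental treatment".

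No reason is given for the two intervals, and nothing elsewhere equalises them or says how onset is to be summarised. Onset does not appear in the Aim of the Study or under Study Outcomes, which list pain by three methods and adverse events. The Statistical Analysis section does not name it either, but gives a rule for quantitative data in general: "descriptive quantitative values will be summarised using mean and standard deviation", and "Comparing between normally distributed data will occur using T- and Paired T-tests", with rank tests for data that are not normally distributed. The Introduction credits the intraligamentary technique with "rapid onset and allowing to start the dental work immediately".

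**The concern.** A time that can be observed only at scheduled probes is rounded up to the next probe. Here the rounding is coarser in the control arm, so the error differs by arm. Its direction is fixed, and averaging over children does not remove it. It favours the experimental technique on a property that the Introduction already presents as an advantage.

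What is at stake is limited to any statement in the thesis or publication that onset was faster with CC-ILA. The only rule available for such a statement is the general one, and neither the t-test nor the Mann-Whitney test allows for different probing grids. Unless the intervals were reported alongside, a reader of the results could not see that part of the difference came from the schedule.

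**Working it through.** **Inputs from the documents.** Probing interval 10 s (CC-ILA) and 30 s (IANB), with a first test immediately after injection (Local Anaesthesia Administration). 25 children per arm (Grouping). Significance at P < 0.05 (Statistical Analysis), taken as two-sided. The plan states no figure for onset, so there is none to reproduce, and every onset distribution below is an assumption.

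**Size of the offset.** Recorded onset = true onset rounded up to the next probe. Take one 30 s interval with onset equally likely anywhere in it:

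- onset in seconds 0–10: CC-ILA reads 10, IANB reads 30, gap 20 s
- onset in seconds 10–20: CC-ILA reads 20, IANB reads 30, gap 10 s
- onset in seconds 20–30: both read 30, gap 0 s

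Mean gap = (20 + 10 + 0)/3 = 10 s. Against true onset the mean delay is 10/2 = 5 s in CC-ILA and 30/2 = 15 s in IANB, and 15 − 5 = 10 s. Relative to the 3–5 minute wait this is 10/300 = 3.3% to 10/180 = 5.6%.

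**When it is not 10 s.** A child already numb at the immediate test has no offset. If 20% are, the mean gap is about 0.8 × 10 = 8 s; if 50% are, about 5 s. In the other direction, if every onset fell within the first 10 s the gap would be 20 s. Simulated gaps for gamma-shaped onset with means from 20 to 180 s were 9.4 to 10.1 s.

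**Effect on a raw comparison with no true difference.** Rounding adds variance of about 10²/12 = 8.3 and 30²/12 = 75. The standard error of the difference is then √[(2·SD² + 8.3 + 75)/25], and the spurious standardised shift is 10 divided by it.

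| Assumed onset mean / SD (s) | Standard error (s) | 10 / SE | Simulated t-test false-positive rate |
|---|---|---|---|
| 90 / 60 | 17.07 | 0.59 | about 9% |
| 90 / 30 | 8.68 | 1.15 | about 20% |
| 60 / 20 | 5.94 | 1.68 | about 39% |
| 30 / 15 | 4.62 | 2.16 | about 50% |

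A noncentral t calculation with these shifts gives 9%, 20% and 38% for the first three rows. It overstates the last (56%), because onset is then not evenly spread within 30 s intervals and the simulated gap is 9.4 s; the simulated rate is the one to use. The rate is driven by the absolute SD, so it can be high even when onset varies considerably relative to its mean (SD half the mean in the last row). With 20% or 50% already numb at the first test, and SD 30 s otherwise, the rate falls to about 9% or 6%. The Mann-Whitney test does not protect: 40% at 60/20 and 46% at 30/15.

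**After correction.** Rounding CC-ILA times up to the next 30 s mark brought the t-test false-positive rate to about 5% in all four rows.

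**The case against.** The strongest reply is that the harm depends on an analysis nobody has planned. Onset appears only within a chairside check that decides when to proceed. It is not an aim or an outcome, and no test is assigned to it. More frequent probing where faster onset is expected is a defensible choice, and the Introduction's remark is background on the technique, not a hypothesis of this trial. If the true difference were minutes, 10 s would not change the conclusion: a simulated true difference of 100 s reads as 110 s. All of this stands, and it keeps the point minor.

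It does not dispose of the point. The time is to be noted, and the general rule is the only guidance for using it.

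A reader might go further and infer that the trial plans a biased test of onset, that the pain comparison or the sample size is compromised, or that the intervals were chosen to favour CC-ILA. The documents support none of these. No onset test is specified, the pain measures do not use the probing grid, the sample size rests on the SEM score, and no reason for the intervals is given.

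It is also fair to say that no statistical correction makes this contrast clean. The operator who performs all injections "cannot be blinded to the type of intervention". The injection sequences before the first probe differ: in CC-ILA a second injection follows ("Same steps will be repeated at the mesiolingual line angle"), while in IANB a buccal infiltration follows the block. Topical gel is placed at the needle site, and numbness is probed on the gingiva. These are further reasons to keep onset descriptive.

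**Conclusion.** The point holds as a minor analysis note, worth considering. The stated schedule makes raw IANB onset read later than raw CC-ILA onset by 0, 10 or 20 s for the same true onset. The mean is about 10 s if onset is spread evenly within intervals, and less if many children are numb at the first test. The direction and the 0/10/20 s pattern follow from the protocol alone. The false-positive rates of about 9% to 50% rest on assumed onset distributions and on a raw between-arm test that the plan permits by its general rule but does not specify. The pain outcomes, the adverse-event outcome and the sample size are untouched.

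**What to change.** Leave the clinical procedure as it is and add one rule to the Statistical Analysis section, for example:

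> *Onset is reported descriptively within each arm together with its probing interval; raw onset times are not compared between arms. Any exploratory between-arm test first puts both arms on the common 30 s grid (CC-ILA times rounded up to the next 30 s mark) or treats onset as interval-censored.*

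This needs no extra probing or data, because the interval follows from the recorded time and the arm. Within-arm reporting is enough on its own and needs no special software. An interval-censored model takes more work, and it should be checked that the named SPSS version can fit it.

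The recode gives up CC-ILA resolution below 30 s. Its mean difference should not be read as unbiased if most CC-ILA onsets fall under 30 s. In the extreme case of CC-ILA onsets spread evenly over 0–10 s (mean 5 s), all are recoded to 30 s, a delay of 25 s against about 15 s in IANB, so the difference is off by 15 − 25 = −10 s, against CC-ILA. Neither option removes the effects of the unblinded operator, the topical gel or the different injection sequences, and the report should say so if any between-arm result is shown.
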